7. RISKS AND DISCOMFORTS

7.1. Blood sampling and intravenous catheter

There are minor risks and discomforts associated with placement of an intravenous line, including the possibility of bleeding, pain, inflammation (redness and swelling), and leaking of contrast agent outside of the vein at the site of the IV. These problems are usually self-limited or require only minor treatments, such as application of an ice-pack or slight pressure for a few minutes.

7.2. Vasodilator stress

Vasodilator-stress with regadenoson and adenosine, as will be performed in this study, has been used routinely for many years for evaluation of known or suspected coronary artery disease in conjunction with myocardial perfusion imaging. During the infusion of the vasodilator stress agent, the patient may experience flushing, chest pain/pressure, nausea, or lightheadedness. If significant symptoms are present, patients will be given aminophylline (reversal agent) IV to relieve these symptoms. There will be continuous monitoring of heart rate, blood pressure, and 12-lead ECG throughout the infusion and recovery. These procedures are routinely performed in patients with CAD, as those in the CIRT trial, and are considered safe.

Regadenoson stress as performed in this study has been used routinely for many years for evaluating patients with known or suspected CAD. The most common side effects associated with the regadenoson bolus include: flushing, chest pain/pressure, shortness of breath, palpitations, headache, mild

hypotension and heart block. These side effects are usually mild and self-limiting. If they are severe in intensity, aminophylline IV (1 mg/kg) will be given as per standard protocol.

Subjects with a history of seizures may receive adenosine. The side effects associated with this product include: facial flushing, headache, sweating, palpitations, chest pain, hypotension, shortness of breath/dyspnea, chest pressure, hyperventilation, head pressure, lightheadedness, dizziness, tingling in arms, numbness, apprehension, blurred vision, burning sensation, heaviness in arms, neck and back pain, nausea, metallic taste, tightness in throat, and pressure in groin. Adenosine is administered as a continuous infusion over 4 minutes and administered in a dose of 0.14mg/kg/min. The half-life of adenosine is less than 10 seconds. If the patient is having symptoms the infusion can be stopped, no further medication is administered, and the symptoms would stop within seconds because the medication would already be cleared from the heart. Therefore, no reversal medication is needed.

Rarely, an aminophylline IV injection may be used to reverse side effects of regadenoson infusion. Aminophylline is generally well tolerated; possible side effects of aminophylline may include nausea, headache, restlessness, convulsions, rapid breathing, a rapid heart rate, and allergic reactions such as rash.

7.3. Radiation risk

The estimated whole body effective radiation dose from each of the ^{13}N -ammonia or $^{82}\text{Rubidium}$ PET scan is ~3-4 mSv⁵⁵, comparable to the annual radiation dose from background radiation sources in North America. Each subject will undergo 2 PET studies during the trial for a total dose of ~6-7 mSv, significantly lower than the average radiation exposure associated with a single conventional myocardial perfusion imaging study using single-photon emission computed tomography (SPECT)⁵⁵.

7.4. Drug side effects and toxicities

There are three adverse reactions >1% that occurred more frequently with Tildrakizumab as compared to placebo in the phase 1 and 2 clinical trials (resurface 1 and 2) which were: upper respiratory infection (14% versus 12% in placebo), injection site reactions (3% versus 2%) and diarrhea (2% versus 1% (Appendix 3) This drug has demonstrated safety over three years (Appendix 4).

7.4.1 Allergic reactions

Symptoms of an allergic reaction to Tildrakizumab may include headache, rash, itching, flushing, swelling, shortness of breath, nausea and sometimes vomiting. Severe allergic reactions can cause dizziness, severe skin reactions, difficulty breathing or swallowing, a decrease in blood pressure, and could be life threatening.

7.5. Echo Contrast (Definity)

In the event of suboptimal imaging windows on echocardiogram, echo contrast (e.g. Definity) may be injected into a vein through the IV prior to conducting the rest and stress echocardiograms. Definity is a perflutren lipid microsphere suspension that is non-iodinated and usually well-tolerated. Rare adverse events, including serious cardiopulmonary or anaphylactoid reactions, have been reported in association with this agent. It will not be administered to patients with known or suspected intracardiac shunts or to patients with known hypersensitivity to echo contrast agents.

7.6. Reproductive risks

Pregnant or breastfeeding patients will be excluded from this study.

7.7. Unknown Risks:

There may be other risks and side effects that are not known at this time.

8. POTENTIAL BENEFITS

8.1. Potential benefits to participating individuals

There are no direct benefits for the patient from taking part in this study. The proposed study will test the important question of whether reducing endothelial cell activation and dysfunction using Tildrakizumab will quantitatively improve coronary flow reserve, a sensitive measure of myocardial ischemia. Thus, this pilot study will provide important and unique mechanistic insights of the capabilities of novel psoriasis therapies to improve key determinants of clinical risk (improve coronary blood flow and reduce ischemia) and, in so doing, improve patient symptoms and quality of life, as well as outcomes.

8.2. Potential benefits to society

Data collected in this trial may provide important mechanistic insights into presumed cardiovascular benefits from novel psoriasis therapies, as well as into the pathophysiology of microvascular dysfunction in psoriasis.

9. MONITORING AND QUALITY ASSURANCE

9.1. Safety monitoring

The PI of the study will monitor the overall safety of the study and will report any adverse effect to the IRB immediately. The PI will also monitor this study to ensure that subjects' human rights, safety, and well-being are protected, that the study is properly conducted in adherence to the current protocol, and study data reported by the investigator/subinvestigator are accurate, complete and verifiable with study-related records such as source documents.

Safety data will be obtained at each study visit from the spontaneous reports by patients of adverse events, vital sign monitoring, physical examinations, 12-lead ECGs and clinical laboratory tests. In addition, telephone follow-up will be conducted to assess for any adverse events. All safety data will be reviewed by the principle investigators of the study (which includes two clinical cardiologists and two clinical dermatologists)

Patients with unexpected abnormalities on the baseline PET scan will be discussed with the patient's PCP/Dermatology physician to decide whether the patient should participate in this pilot trial. The findings will be discussed with the patient and the patient's primary physician in order to facilitate an appropriate management plan. If a patient is excluded on safety grounds, we do not think that this will affect our ability to determine the effect of Tildrakizumab on myocardial blood flow.

The safety of Tildrakizumab will be assessed with respect to the following end points: (1) death from any cause, (2) the composite of death from any cause or any cardiovascular hospitalization, (3) frequency of symptomatic documented arrhythmia, (4) serious adverse events related to the study drug and clinically significant laboratory abnormalities.

9.2. Treatment Compliance

Subject compliance to treatment regimen will be assessed by confirmation of the full administration of each dose being administered during the four Dermatology clinical assessments.

9.3. Discontinuation criteria for individual subjects

Discontinued subjects are those who are enrolled in the study and for whom study treatment is terminated prematurely for any reason. The subject is free to withdraw from the study treatment and/or study for any reason and at any time without giving reason for doing so and without penalty or prejudice. The investigator is also free to terminate a subject's involvement in the study at any time if the subject's clinical condition warrants it.

Subjects will be discontinued if:

- Subject experiences a serious or intolerable adverse event
- Subject has severe disease and has to be intervened upon based on the imaging tests
- In the Investigator's opinion, the subject is non-compliant with the protocol requirements
- Subject's health would be jeopardized by continued participation
- Subject wishes to withdraw consent
- Investigator elects to end the study

9.4. Adverse event reporting guidelines

9.4.1 Definition of Adverse Events (AEs)

An adverse event (AE) is defined as any untoward medical occurrence in a subject administered a study drug, and which does not necessarily have a causal relationship with this treatment. An AE can therefore be any unfavorable and unintended sign (including an abnormal laboratory finding), symptom, or disease temporally associated with the use of a study drug, whether or not related to the study drug.

An abnormality identified during a medical test (e.g., laboratory parameter, vital sign, ECG data, physical exam) should be defined as an AE only if the abnormality meets one or more of the following criteria:

- Induces clinical signs or symptoms
- Requires active intervention
- Requires interruption or discontinuation of study medication
- The abnormality or investigational value is clinically significant in the opinion of the investigator

9.4.2 Definition of Serious Adverse Events (SAEs)

A serious AE is any untoward medical occurrence that, at any dose:

- Results in death,

- Is life threatening (an event in which the subject is at risk of death at the time of the event; it does not refer to an event which hypothetically might have caused death if it was more severe),
- Results in persistent or significant disability/incapacity,
- Results in congenital anomaly, or birth defect,
- Requires inpatient hospitalization or leads to prolongation of hospitalization (hospitalization for treatment/observation/examination caused by AE is to be considered as serious)
- Other medically important events

Medical and scientific judgment should be exercised in deciding whether expedited reporting is appropriate in other situations, such as important medical events that may not be immediately life-threatening or result in death or hospitalization but may jeopardize the subject or may require intervention to prevent one of the other outcomes listed in the definition above. These events, including those that may result in disability, should also usually be considered serious.

9.4.3 Criteria for Causal Relationship to the Study Drug

Adverse events that fall under either "Possible" or "Probable" should be defined as "adverse events whose relationship to the study drugs could not be ruled out."

Causal relationship to the study drug	Criteria for causal relationship
Not Related	A clinical event, including laboratory test abnormality, with a temporal relationship to drug administration which makes a causal relationship improbable, and/or in which other drugs, chemicals or underlying disease provide plausible explanations.
Possible	A clinical event, including laboratory test abnormality, with a reasonable time sequence to administration of the drug, but which could also be explained by concurrent disease or other drugs or chemicals. Information on drug withdrawal may be lacking or unclear.
Probable	A clinical event, including laboratory test abnormality, with a reasonable time sequence to administration of the drug, unlikely to be attributed to concurrent disease or other drugs or chemicals, and which follows a clinically reasonable response on re-administration (re-challenge) or withdrawal (de-challenge).

9.4.4 Criteria for Defining the Severity of an Adverse Event

The following standard with 3 grades is to be used to measure the severity of adverse events, including abnormal clinical laboratory values.

- Mild: No disruption of normal daily activities
- Moderate: Affect normal daily activities

- Severe: Inability to perform daily activities

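### Section 9.4.4 grades laboratory adverse events by effect on daily activities, so a symptom-free one that leaves activities undisturbed can only be recorded as Mild

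*Combined protocol and SAP*

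**What the plan says.** Section 9.4.4 introduces its severity scale with the sentence "The following standard with 3 grades is to be used to measure the severity of adverse events, including abnormal clinical laboratory values". The grades are:

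- "Mild: No disruption of normal daily activities"
- "Moderate: Affect normal daily activities"
- "Severe: Inability to perform daily activities"

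Section 9.4.1 decides which test abnormalities become AEs at all. An abnormality found on a medical test "should be defined as an AE only if the abnormality meets one or more of the following criteria". There are four criteria. One is that it produces signs or symptoms. The other three are "Requires active intervention", a need to pause or stop the study drug, and "The abnormality or investigational value is clinically significant in the opinion of the investigator".

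Section 9.1 lists four safety endpoints. The fourth covers "serious adverse events related to the study drug and clinically significant laboratory abnormalities".

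Section 5.4 names the tests: hs-CRP, hs-troponin, a metabolic panel, a blood count and lipids, at baseline and at the end of treatment. The documents contain no numeric bands, multiples of reference limits, toxicity table or investigator override for the severity of a laboratory value.

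**The concern.** A daily-activity scale works for events that the patient feels. A laboratory value affects activities only through the symptoms it causes or the management it leads to, and many abnormalities of a blood count, a metabolic panel or troponin cause no symptoms. Section 9.4.1 deliberately brings such findings in as AEs when they matter clinically, but 9.4.4 then grades them on a feature they do not have.

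What is at stake is the descriptive value of the severity field. The study is a single-arm, open-label pilot (section 3.1, Study Design), so its safety data will be read descriptively, with no control group for reference. For non-serious laboratory AEs, severity is the only ranking the protocol provides, and here it cannot separate a marginal value from an extreme one.

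**Working it through.** No arithmetic decides this point. The check sets the sections side by side.

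**Step 1: which laboratory AEs can be symptom-free.** Taking the four criteria of 9.4.1 in turn:

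| Criterion in 9.4.1 | Can be met without symptoms? |
|---|---|
| Produces signs or symptoms | No, taking it to mean effects the patient shows or feels |
| Active intervention needed | Yes |
| Study drug paused or stopped | Yes |
| Investigator judges it clinically significant | Yes |

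Three of the four routes are open to a symptom-free abnormality. One that meets none of the four is not an AE and receives no grade.

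**Step 2: which grade fits.** Take a laboratory AE that entered by one of those three routes and has not disturbed daily activities.

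| Grade in 9.4.4 | What it requires | Met? |
|---|---|---|
| Mild | No disruption of activities | Yes |
| Moderate | Some effect on activities | No |
| Severe | Activities not possible | No |

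Only Mild fits. The size of the deviation does not enter any of the three definitions, so two results of the same test, one marginal and one extreme, receive the same grade.

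**Step 3: where the grade is used.**

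- Safety endpoints (9.1): defined by type of event. The laboratory part of endpoint (4) turns on clinical significance.
- Discontinuation (9.3): turns on seriousness, tolerability, risk to health, compliance, consent and similar grounds.
- Serious AEs (9.4.2) and their reporting to the IRB (9.4.5): turn on seriousness, which includes a category for medically important events.
- Causality (9.4.3): assessed separately.
- Follow-up (9.4.6): continues until the event resolves, loses clinical significance or becomes chronic and characterised.
- Statistical analysis (6.3 and 6.4): plans no AE tabulation, by severity or otherwise.

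None of these depends on the 9.4.4 grade. The distortion stays in the recorded grade and in any later summary that uses it.

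**Step 4: exposure.** After dosing starts, Table 1 schedules laboratory tests once, at week 24. With the planned 35 patients that is 35 × 1 = 35 scheduled post-dose draws, plus any unscheduled ones. Section 4.3 places the last dose at week 16, so a scheduled post-dose result comes too late to pause or stop dosing. For those draws, the symptom-free routes that matter in practice are intervention and clinical significance.

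**The case against.** The strongest reply is that nothing in the plan depends on this grade, and Step 3 bears that out. Several stronger readings are tempting, and the documents do not support them.

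- A reader might infer that safety endpoint (4) is understated. It is not. A laboratory finding counts there because it is clinically significant, and it counts in full even when labelled Mild.
- A reader might infer that the plan will publish a severity table biased by construction. No such table is planned. The bias reaches only a summary that someone later builds on the grade.
- A reader might infer that an extreme silent value could escape attention. Severity and seriousness are separate here. Such a value can still be classed as serious under the medically important category in 9.4.2 and reported under 9.4.5.
- A reader might infer that the scale is defective because it has no grade for life-threatening or fatal events. Section 9.4.2 captures both as serious, and death is also safety endpoint (1) and part of endpoint (2). Having three levels is a choice, not an error.
- A reader might infer that every symptom-free abnormality is recorded as Mild. Those that fail 9.4.1 are not graded. Where managing the abnormality itself disrupts activities, as a hospital stay would, a higher grade could be argued; the text is silent.

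It is also fair to say that exposure is small, that the numeric results are kept and could be regraded later, and that changes in hs-CRP and hs-troponin are analysed anyway under secondary endpoint (6).

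All of this limits the consequence. It does not remove the defect: a non-serious, clinically significant laboratory AE has no other size-based classification in the documents, and the stated rule gives it a grade that carries no information about size.

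**Conclusion.** The point holds within narrow limits. For laboratory AEs that qualify under 9.4.1 without symptoms and do not disrupt daily activities, 9.4.4 permits only the lowest grade. The recorded severity of these events is uninformative and can err only downwards.

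Within that class every event is affected. How many events that will be cannot be estimated, because the documents give no expected rate of laboratory AEs; with one scheduled post-dose draw per patient it is probably few. Safety endpoint (4), the handling of serious AEs, discontinuation, follow-up and the primary CFR analysis are untouched.

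The conclusion assumes that 9.4.4 is applied as written and that no grading rule for laboratory values exists outside these documents. Minor priority.

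**What to change.** Amend one paragraph in 9.4.4. Restrict the daily-activity scale to symptomatic events, and state that laboratory AEs are graded by a value-based standard, such as a published laboratory toxicity table or multiples of the reference limits. The sponsor should choose the standard and fix it before the data are reviewed. No additional grade for life-threatening or fatal events is needed.

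The cost is small. The results are already collected, so grades can be assigned in the analysis program with no extra visit, sample or patient burden. The one downside is that some laboratory AEs will be shown at a higher grade than under the present rule.

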9.4.5 Reporting of Serious Adverse Events (SAEs)

In the case of a serious adverse event (SAE), the investigator should submit a report to the IRB within 5 working days/7 calendar days of the date the investigator first becomes aware of the problem as per Partners policy.

9.4.6 Follow-up to Adverse Events

All adverse events occurring during the study are to be followed up until resolved or judged to be no longer clinically significant, or until they become chronic to the extent that they can be fully characterized.

If during adverse event follow-up, the adverse event progresses to an "SAE," or if a subject experience a new SAE, the investigator must immediately report the information to the sponsor.

9.4.7 Procedure in Case of Pregnancy

If a woman becomes pregnant during the study dosing period or within 30 days from the discontinuation of dosing, the investigator will report the information to the PHRC as if it is an SAE. The expected date of delivery or expected date of the end of the pregnancy, last menstruation, estimated fertility date, pregnancy result and neonatal data etc., should be included in this information.

The investigator will follow the medical status of the mother, as well as the fetus, as if the pregnancy is an SAE.

When the outcome of the pregnancy falls under the criteria for SAEs [spontaneous abortion, induced abortion, stillbirth, death of newborn, congenital anomaly (including anomaly in a miscarried fetus)], the investigator should respond in accordance with the report procedure for SAEs. Additional information regarding the outcome of a pregnancy (which is categorized as an SAE) is mentioned below:

- "Spontaneous abortion" includes abortion and missed abortion.
- Death of an infant within 1 month after birth should be reported as an SAE regardless of its relationship with the study drug.
- If an infant dies more than 1 month after the birth, it should be reported if a relationship between the death and intrauterine exposure to the study drug is judged as "possible" by the investigator.
- In the case of a delivery of a living newborn, the "normality" of the infant is evaluated at the birth. "Normality" of the miscarried fetus is evaluated by visual examination unless test results which indicate a congenital anomaly are obtained prior to miscarriage.

References

- 1 Hansson GK, Robertson A-KL, Söderberg-Nauclér C. Inflammation and atherosclerosis. *Annu Rev Pathol* 2006; **1**: 297–329.
- 2 Libby P. Inflammation in atherosclerosis. *Arterioscler Thromb Vasc Biol* 2012; **32**: 2045–2051.

Appendix

Appendix 1: Therapy-specific washout periods

Therapy	Length of washout period
Systemic Therapy	
Biologics	
Etanercept	30 days
Adalimumab and Infliximab	45 days
Anti-IL17 Biologics (Including Secukinumab, bimekizumab, ixekizumab, brodalumab)	60 days
Ustekinumab	60 days
Non-biologics	
Apremilast, cyclosporine, corticosteroids, methotrexate, acitretin, mycophenolate, thioguanine, hydroxyurea, sirolimus, sulfasalazine, azathioprine, fumaric acid esters	30 days
Phototherapy	
Ultraviolet B [UVB], psoralen and ultraviolet A radiation [PUVA]	30 days
Topical Therapy	
Medium and High potency topical corticosteroids, vitamin D analog preparations (calcipotriene, calcitriol), calcineurin inhibitors (pimecrolimus, tacrolimus)	
-Exceptions: Unmedicated emollients (eg, Eucerin®) for body lesions and non-medicated shampoos for scalp lesions (Subjects should not use these topical treatments within 24 hours prior to the clinic visit.)	14 days
Mild potency topical steroids** will be permitted for use limited to the face, neck, axilla, and/or genitalia as rescue medication	

* Examples of Medium and High Potency Topical Steroids: Diprolene Cream AF (betamethasone), Halong Ointment (halcinonide), Ultravate Cream (halobetasol), Psorcon (E) Ointment (diflorasone), Vanos Cream (fluocinonide), Cordran Ointment (flurandrenolide), Clobex Lotion/Spray/Shampoo (clobetasol), Cormax Cream/Solution (clobetasol), Temovate Cream/Ointment/Solution (clobetasol), Elocon Ointment (mometasone), Tropicort Cream (desoximetasone), Tropicort Gel (desoximetasone), Tropicort LP Cream (desoximetasone).

**Examples of Mild Potency Topical Steroids: Synalar Ointment (flucinolone acetonide), Cutivate Ointment (fluticasone), Verdeso Foam (desonide), Desonate Gel (desonide), DesOwen Lotion (desonide), Aclovate Cream/Ointment (aclometasone), Hydrocortisone Cream

